Event	Scr ¹	Biopsy ²			Biopsy ²			Biopsy ²				Pre- Impl.	2 nd Injection (Hosp.)				llow 3 da	-up ıy)	2 nd Injection Follow-up (±7days)								Long Term Follow Up ³ (±7days)				
Assessment	≤45d pre- biopsy	3 to 1 day	Biopsy	1 day	,	14 to 10d	D0	Inpt.4	Disch.5	D7	D14	D28	2mo	3mo	6mo (14 to 10 day)	8mo	9mo	12mo	15mo	18mo ⁶ EOS	24mo Call	30mo Visit	36mo Call	42mo Visit							
ICF ⁷	Х				ell																										
I/E Criteria ⁸	Х	Х			al c	Х																									
Med. Hist. ⁹	Х	Х			Ren																										
ECG	Х				KS:	Х						Х			Х			Х		Х											
Comp. Phy. Exam ¹⁰	Х				vee																										
Interim Phy Exam ¹⁰		Х			14	Х						Х			Х			Х		Х		Х		Х							
Vital Signs ¹¹	Х	Х	Х	Х	4	Х	X ¹²	Х	Х	Х	Х	Х	Х	Х	Х	Х	Х	Х	Х	Х											
Ultrasound/CT			Х	Х		X ¹³	Х	Х	X ¹⁴						Х																
MRI	X ¹⁵																			Х											
Renal Scint.						Х									Х			Х		Х											
Biopsy ¹⁶		Х	X ¹⁶																												
Admit to Hosp.			Х				Х																								
Injection NKA ¹⁷							Х																								
Discharge				Х					X ⁵																						
AE's ¹⁸		Х	Х	Х		Х	Х	Х	Х	Х	Х	Х	Х	Х	Х	Х	Х	Х	Х	Х	Х	Х	Х	Х							
ConMeds	Х	Х	Х	Х		Х	Х	Х	Х	Х	Х	Х	Х	Х	X	Х	Х	Х	Х	Х											
KDQoL Survey ¹⁹						Х						Х		X	Х		Х	Х	Х	Х		Х		Х							

Time and Events Schedule: Patients receiving Second Dose NKA Only Laparoscopic Approach

¹ Screening assessments should be conducted within 45 days before the injection; if assessments fall outside of the 45 day window, rescreening should be conducted as discussed in Section 11.1

² The biopsy will only be obtained if there are not enough frozen SRC from the previous study. If there is enough for NKA product to be made skip this visit and proceed to Pre-Injection visit (14d to 10d).

- ³ Monthly visit dates for follow-up visits should be based on the calendar day (\pm 7 days).
- ⁴ Inpatient hospital days, Days 1 and possibly Days 2 and 3.
- ⁵ The patient will be discharged as early as Day 2 and as late as Day 4 following laparoscopic injection
- ⁶ Conduct End-of-Study (EOS) assessments at the 18 mo visit post second injection, or when the subject discontinues from the study (See Section 11.4)
- ⁷ The informed consent form (ICF) must be signed prior to conducting any study-specific procedures.
- ⁸ Appropriate selected Inclusion/Exclusion criteria should be reviewed at Screening, and pre-injection.
- ⁹ Medical and surgical history should be obtained at Screening.
- ¹⁰ The physical examination (PE) is described in Section 12.2.2.

Confidential

¹¹ Vital signs include heart rate, resting BP, and body temperature. (See section 12.2.3)

- ¹² Vital signs should be measured throughout the procedure.
- ¹³ An ultrasound should be performed 10 to 14 days before injection to verify continued eligibility and on Day 1 following injection to verify lack of adverse events/safety concerns.
- ¹⁴ If clinically indicated due to, for example, bleeding during the procedure or a drop in hemoglobin, an ultrasound may be performed prior to discharge to assess safety concerns.
- ¹⁵ To determine kidney size and volume, an MRI study should be performed between screening and the injection.
- ¹⁶ The patient may be released same day as biopsy per site standard practice, if released same day as biopsy skip day 1 procedures after biopsy.
- ¹⁷ NKA product should be handled and injected according to procedures described in the Study Reference Manual.
- ¹⁸ Record NKA-related SAE's, NKA-related and significant CKD-related AE's reported by the patient at the visit, and ongoing CKD-specific medications.
- ¹⁹ KDQOL Survey will be completed at pre-injection and at day 28 and months 3, 6, 9, 12, 15, 18, 30 and 42 months after second NKA injection.

Event	Scr ¹	Biopsy ²			Biopsy ²			Biopsy ²			Biopsy ²				Pre- Impl.	2 nd Injection		Follow- (± 3 da	up y)			2no	d Injectio	n Fol	llow-	up (±7	'days)			Long Follo (±70	Term w Up ³ lavs)	
Assessment	≤45d pre- biopsy	3 to 1 day	Biopsy	1 day		14 to 10d	D0 ⁴	D1	D7	D14	D28	2mo	3mo	6mo (14 to 10 day)	8mo	9mo	12mo	15mo	18mo ⁵ EOS	24mo Call	30mo Visit	36mo Call	42mo Visit									
ICF ⁷	Х				A																											
I/E Criteria ⁸	Х	Х			NK	Х																										
Med. Hist. ⁹	Х	Х			ofl																											
ECG	Х				ure	Х					Х			Х			Х		Х													
Comp. Phy. Exam ¹⁰	Х				fact																											
Interim Phy Exam ¹⁰		Х			anuf	Х					Х			Х			Х		Х		Х		Х									
Vital Signs ¹¹	Х	Х	Х	Х	l m	Х	X ¹²		Х	Х	Х	Х	Х	Х	Х	Х	Х	Х	Х													
Ultrasound/CT			Х	Х	anc	X ¹³	X ¹⁴							Х																		
MRI	X ¹⁵				ion														Х													
Renal Scint.					lect	Х								Х			Х		Х													
Biopsy ¹⁶		Х	X ¹⁶		l se																											
Admit to Hosp.			Х		cel		Х																									
Injection NKA ¹⁷					enal		Х																									
Discharge				Х	: Re		X ⁴																									
Telephone Call					eks			X ⁶												Х		Х										
AE's ¹⁸		Х	Х	Х	we	Х	Х	Х	Х	Х	Х	Х	Х	Х	Х	Х	Х	Х	Х	Х	Х	Х	Х									
ConMeds	Х	Х	Х	Х	-14	Х	Х	Х	Х	Х	Х	Х	Х	Х	Х	Х	Х	Х	Х													
KDOoL Survey ¹⁹				1	4	X				İ	X		X	X		X	X	X	X	l I	X		X									

Time and Events Schedule: Patients receiving Second Dose NKA Only Percutaneous Approach

 KDQoL Survey¹⁹
 X
 X
 X
 X
 X
 X
 X
 X
 X
 X
 X
 X
 X
 X
 X
 X
 X
 X
 X
 X
 X
 X
 X
 X
 X
 X
 X
 X
 X
 X
 X
 X
 X
 X
 X
 X
 X
 X
 X
 X
 X
 X
 X
 X
 X
 X
 X
 X
 X
 X
 X
 X
 X
 X
 X
 X
 X
 X
 X
 X
 X
 X
 X
 X
 X
 X
 X
 X
 X
 X
 X
 X
 X
 X
 X
 X
 X
 X
 X
 X
 X
 X
 X
 X
 X
 X
 X
 X
 X
 X
 X
 X
 X
 X
 X
 X
 X
 X
 X
 X
 X
 X
 X
 X
 X
 X
 X
 X
 X
 X
 X
 X
 X
 X
 X
 X
 X

² The biopsy will only be obtained if there are not enough frozen SRC from the previous study. If there is enough for NKA product to be made skip this visit and proceed to Preinjection visit (14d to 10d).

³ Monthly visit dates for follow-up visits should be based on the calendar day (\pm 7 days).

⁴ The patient may be discharged same day as percutaneous injection.

⁵ Conduct End-of-Study (EOS) assessments at the 18 mo visit post second injection, or when the subject discontinues from the study (See Section 11.4)

⁶ 24hours post discharge a follow up phone call from the clinic will be conducted to do a wellness check on the subject.

⁷ The informed consent form (ICF) must be signed prior to conducting any study-specific procedures.

⁸ Appropriate selected Inclusion/Exclusion criteria should be reviewed at Screening, and pre-injection.

⁹ Medical and surgical history should be obtained at Screening.

 10 The physical examination (PE) is described in Section 12.2.2 .

Confidential

¹¹ Vital signs include heart rate, resting BP, and body temperature. (See section 12.2.3)

- ¹² Vital signs should be measured throughout the procedure.
- ¹³ An ultrasound should be performed 10 to 14 days before injection to verify continued eligibility and on Day 1 following injection to verify lack of adverse events/safety concerns.
- ¹⁴ If clinically indicated due to, for example, bleeding during the procedure or a drop in hemoglobin, an ultrasound may be performed prior to discharge to assess safety concerns.
- ¹⁵ To determine kidney size and volume, an MRI study should be performed between screening and the injection.
- ¹⁶ The patient may be released same day as biopsy per site standard practice, if released same day as biopsy skip day 1 procedures after biopsy.
- ¹⁷ NKA product should be handled and injected according to procedures described in the Study Reference Manual.
- ¹⁸ Record NKA-related SAE's, NKA-related and significant CKD-related AE's reported by the patient at the visit, and ongoing CKD-specific medications.
- ¹⁹ KDQOL Survey will be completed at pre-injection and at day 28 and months 3, 6, 9, 12, 15, 18, 30 and 42 months after second NKA injection.

Event	Scr ¹	Biopsy			Biopsy		Biopsy		Biopsy			Biopsy			Biopsy			Biopsy			Biopsy			Biopsy			Biopsy			Biopsy			Biopsy			Biopsy			Biopsy			Biopsy			Biopsy			Biopsy		Biopsy		opsy Pi In		Pre- Impl.	injection (Hosp.)			Follow-up (± 3 day)		1 st Injection Follow-up (±7days)		Pre-2 nd Injection 2	n 2 nd Injection (Hosp)			2 nd Injection Follow-up (± 3 day)			Follow-up (±7days)					Long Term Follow Up ³ (±7days)			
Assessment	≤45d pre- biopsy	3 to 1 day	Biopsy	1 day		14 to 10d	D0	Inpt.4	Disch.5	D7	D14	D28	2mo	3mo	6mo (14 to 10 day)	D0	Inpt. ⁴	Disch ⁵	D7	D14	D28	8mo	9mo	12mo	15mo	18mo ⁶ EOS	24mo Call	30mo Visit	36mo Call	42mo Visit																																															
ICF ⁷	Х				KA																																																																								
I/E Criteria ⁸	Х	Х			fΝ	Х																																																																							
Med. Hist. ⁹	Х	Х			re o																																																																								
ECG	Х				ic tu:	Х						Х			Х									Х		Х																																																			
Comp. Phy. Exam ¹⁰	Х				nufa																																																																								
Interim Phy Exam ¹⁰		Х			mar	Х						Х			Х									Х		Х		Х		Х																																															
Vital Signs ¹¹	Х	Х	Х	Х	pu	Х	X ¹²	Х	Х	Х	Х	Х	Х	Х	Х	X^{12}	Х	Х	Х	Х	Х	Х	Х	Х	Х	Х																																																			
Ultrasound/CT			Х	Х	on a	X ¹³	Х	Х	X ¹⁴						Х	Х	Х	X ¹⁴																																																											
MRI	X ¹⁵				ectie																					Х																																																			
Renal Scint.					sele	Х									Х									Х		Х																																																			
Biopsy ¹⁶		Х	X^{16}		cell																																																																								
Admit to Hosp.			Х		nal (Х									Х																																																													
Inject NKA ¹⁷					Rer		Х									Х																																																													
Discharge				Х	ks:				X ⁵									Х																																																											
AE's ¹⁸		Χ	Х	Х	wee	Х	Х	Х	X	Х	Х	Х	Χ	Х	Х	Х	Х	Х	Х	Х	Х	Х	Х	Х	Х	Х	Х	Х	Χ	Χ																																															
ConMeds	Х	Χ	Х	Х	14 1	Х	Χ	Χ	X	Х	Х	Χ	Χ	Х	Х	Х	Х	Х	Х	Χ	Х	Х	Χ	Χ	Х	Х																																																			
KDQoL Survey ¹⁹					4	Х						Х		Х	Х						Х		Х	Х	Х	Х		Х		Х																																															

Time and Events	Schedule: New	Patients Re	eceiving Lapar	roscopic Approach
				 

¹ Screening assessments should be conducted within 45 days before the injection; if assessments fall outside of the 45 day window, rescreening should be conducted as discussed in Section 11.1

² If at 6 month visit the PI determines a second dose is not going to be completed patient should return to the clinic at month 9 visit and resume TES.

³ Monthly visit dates for long-term follow-up visits should be based on the calendar day (\pm 7 days).

⁴ Inpatient hospital days, Days 1 and possibly Days 2 and 3.

⁵ The patient will be discharged as early as Day 2 and as late as Day 4 following laparoscopic injection

⁶ Conduct End-of-Study (EOS) assessments at the 18 mo visit post second injection, or when the subject discontinues from the study (See Section 11.4)

⁷ The informed consent form (ICF) must be signed prior to conducting any study-specific procedures.

⁸ Appropriate selected Inclusion/Exclusion criteria should be reviewed at Screening, and pre-injection.

⁹ Medical and surgical history should be obtained at Screening.

 10 The physical examination (PE) is described in Section 12.2.2 .

¹¹ Vital signs include heart rate, resting BP, and body temperature. (See section 12.2.3)

¹² Vital signs should be measured throughout the procedure.

Confidential

¹³ An ultrasound should be performed 10 to 14 days before injection to verify continued eligibility and on Day 1 following injection to verify lack of adverse events/safety concerns.

¹⁴ If clinically indicated due to, for example, bleeding during the procedure or a drop in hemoglobin, an ultrasound may be performed prior to discharge to assess safety concerns.

¹⁵ To determine kidney size and volume, an MRI study should be performed between screening and the injection.

¹⁶ The patient may be released same day as biopsy per site standard practice, if released same day as biopsy skip day 1 procedures after biopsy.

¹⁷ NKA product should be handled and injected according to procedures described in the Study Reference Manual.

¹⁸ Record NKA-related SAE's, NKA-related and significant CKD-related AE's reported by the patient at the visit, and ongoing CKD-specific medications.

¹⁹ KDQOL Survey will be completed at pre-injection and at day 28 and months 3, 6, 9, 12, 15, 18, 30 and 42 months after second NKA injection.

Event	Scr ¹		Biopsy	,		Pre- Impl.	Inje	1 st ection	F	Follov (± 3 c	v-up lay)	1 Inje Fol u (±7d	st ction low- p lays)	Pre-2 nd Injection ²	2 Inje	nd ction	2 nd] Fol (±	Injec llow- 3 da	etion -up ay)		2 nd Iı ı	ijectio ip(±70	n Foll lays)	low		Long Follo (±70	Term w Up ³ days)	1 3
Assessment	≤45d pre- biopsy	3 to 1 day	Biopsy	1 day		14 to 10d	D0 ⁴	D1	D7	D14	D28	2mo	3mo	6mo (14 to 10 day)	D0 ⁴	D1	D7	D14	D28	8mo	9mo	12mo	15mo	18mo ⁵ EOS	24mo Call	30mo Visit	36mo Call	42mo Visit
ICF ⁷	Х				√																							
I/E Criteria ⁸	Х	Х			NK	Х																						
Med. Hist. ⁹	Х	Х			of]																							
ECG	Х				ure	Х					Х			Х								Х		Х				
Comp. Phy. Exam ¹⁰	Х				fact																							
Interim Phy Exam ¹⁰		Х			anu	Х					Х			Х								Х		Х		Х		Х
Vital Signs ¹¹	Х	Х	Х	Х	d m	Х	X ¹²		Х	Х	Х	Х	Х	Х	Х		Х	Х	Х	Х	Х	Х	Х	Х				
Ultrasound/CT			Х	Х	an	X ¹³	X ¹⁴							Х	X ¹⁴													
MRI	X ¹⁵				tion																			Х				
Renal Scint.					elect	Х								Х								Х		Х				
Biopsy ¹⁶		Х	X ¹⁶		ll se																							
Admit to Hosp.			Х		ce		Х								Х													
Injection NKA ¹⁷					ena		Х								Х													
Discharge				Х	: R																							
Telephone Call					eks			X6								X ⁶									Х		Х	
AE's ¹⁸		Х	Х	Х	W.	Х	Х	Х	Х	Х	Х	Х	Х	Х	Х	Х	Х	Х	Х	Х	Х	Х	Х	Х	Х	Х	Х	Х
ConMeds	Х	Х	Х	Х	-14	Х	Х	Х	Х	Х	Х	Х	Х	Х	Х	Х	Х	Х	Х	Х	Х	Х	Х	Х				
KDQoL Survey ¹⁹					4	Х					Х		Х	Х					Х		Х	Х	Х	Х		Х		Х

Гime and	Events	Schedule:	New	Patients	Receiving	Percutaneous	Approach
					0		11

¹ Screening assessments should be conducted within 45 days before the injection; if assessments fall outside of the 45 day window, rescreening should be conducted as discussed in Section 11.1

² If at 6 month visit the PI determines a second dose is not going to be completed patient should return to the clinic at month 9 visit and resume TES.

³ Monthly visit dates for long-term follow-up visits should be based on the calendar day (\pm 7 days).

⁴ The patient may be discharged same day as percutaneous injection.

⁵ Conduct End-of-Study (EOS) assessments at the 18 mo visit post second injection, or when the subject discontinues from the study (See Section 11.4)

⁶ 24hours post discharge a follow up phone call from the clinic will be conducted to do a wellness check on the subject.

⁷ The informed consent form (ICF) must be signed prior to conducting any study-specific procedures.

⁸ Appropriate selected Inclusion/Exclusion criteria should be reviewed at Screening, and pre-injection.

⁹ Medical and surgical history should be obtained at Screening.

¹⁰ The physical examination (PE) is described in Section 12.2.2.

Confidential

¹¹ Vital signs include heart rate, resting BP, and body temperature. (See section 12.2.3)

- ¹² Vital signs should be measured throughout the procedure.
- ¹³ An ultrasound should be performed 10 to 14 days before injection to verify continued eligibility and on Day 1 following injection to verify lack of adverse events/safety concerns.
- ¹⁴ If clinically indicated due to, for example, bleeding during the procedure or a drop in hemoglobin, an ultrasound may be performed prior to discharge to assess safety concerns.
- ¹⁵ To determine kidney size and volume, an MRI study should be performed between screening and the injection.
- ¹⁶ The patient may be released same day as biopsy per site standard practice, if released same day as biopsy skip day 1 procedures after biopsy.
- ¹⁷ NKA product should be handled and injected according to procedures described in the Study Reference Manual.
- ¹⁸ Record NKA-related SAE's, NKA-related and significant CKD-related AE's reported by the patient at the visit, and ongoing CKD-specific medications.
- ¹⁹ KDQOL Survey will be completed at pre-injection and at day 28 and months 3, 6, 9, 12, 15, 18, 30 and 42 months after second NKA injection.

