4 TIME AND EVENTS SCHEDULE: LABORATORY ASSESSMENTS

Event	Scr ¹	Bi	opsy	y ²		Pre-		Inject	tion $(1)^{3}$	Fo	ollow	-up	1 st Inj Follo	ection w-up	Pre-2 nd Injectio	2	nd Injec (Hosp.	tion .) ³	2 nd Fo	Injeo ollow	ction /-up		F	Follow (± 7 d	-up ay)		Long	Term (± 7	Follo [,] day)	w Up
						mpi.	 	(1105)	J.)	(-	- 5 u	iy)	(± 7	day)	n		r		(=	± 3 d:	ay)						24	20	26	12
Laboratory Assessment	≤45d pre- biopsy	3 to 1 day	Biopsy	1 day		14 to 10 days	D0	Inpt ⁴	Disch ⁵	D7	D14	D28	2 mo	3mo	6mo (14 to 10 day)	D0	Inpt ^{.4}	Disch ⁵	D7	D14	D28	8mo	9mo	12mo	15mo	18mo EOS ⁶	24mo Call	30mo Visit	Call	42mo Visit
Chemistry ⁷					J.																									
 Std. panel 	Х	Х		Х	io e	Х	Х	Х	Х	Х	Х	Х	Х	Х	Х	Х	Х	Х	Х	Х	Х	Х	Х	Х	Х	Х		Х		Х
• Renal	Х	Х		Х	ture	Х	Х	Х	Х	Х	Х	Х	Х	Х	Х	Х	Х	Х	Х	Х	Х	Х	Х	Х	Х	Х		Х		Х
 Pregnancy test⁸ 	Х	Х			fac	Х			l						Х															
• HIV, HBV, HCV	Х	Х			nun				l																					
 Lipid Panel 	Х				ma	Х									Х															
Hematology ⁹	Х	Х		Х	pu	Х		Х	X	Х	Χ	Х	Х	Х	Х		Х	Х	Х	Х	Х	Х	Х	Х	Х	Х				
• Multiple ¹⁰			Χ		n a		Х									Х														
Coag. Status	X	Χ			ctio	X									Х															
Urinalysis					cA																									
• 24 hour	X				II se									X									Χ	Х	Х	Χ				
 Spot urine 	Х	Х			cel	Х				Х		Х	Х	Х	Х				Х		Х	Х	Х	Х	Х	Х		Х		X
 Test stick 				Х	nal	Х	X ¹¹								Х	X^{11}														
Add. Tests:					Re																									
• HbA1c	X				S:																			X		Х		Х		X
Beta 2microblobulin ¹²	Х	Х			week	Х						Х			Х						Х			Х		Х				
• iPTH	Х	Х			14	Х			l			Х		Х	Х						Х			Х		Х				
• Research (reserve) Samples ¹³	Х	х			4	Х						Х	Х	Х	Х						Х	Х	X	Х	Х	Х		Х		Х

¹ Screening assessments should be conducted within the 45 days prior to the injection; if assessments fall outside of the 45 day window, rescreening should be conducted as discussed in Section 11.1.

² Patient may be released same day as biopsy per site standard practice, if released same day as biopsy skip day 1 procedures after biopsy. Note that returning patients may not need a biopsy to be completed and will go from screening to the pre-injection visit.

³ Patients receiving percutaneous approach will have Day 0 lab assessments and then skip to day 7 assessments.

⁴ Inpatient Hospital days, Days 1 and possibly Days 2 and 3 depending on day of discharge.

⁵ The patient will be discharged as early as Day 2 and as late as Day 4 following laparoscopic injection, or Day 1 following percutaneous injection. Refer to Section 11.4 for discharge instructions.

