9 STUDY DESIGN

An overview of the study flow is shown in the diagram below.

After patients have signed the ICF, they should be screened for entry into the study. Screening assessments include laboratory assessments, physical examination, and an ECG and MRI study, all of which must be performed before the biopsy is taken. If the patient meets all I/E criteria, a biopsy of the left/right kidney should be taken within 45 days of the first screening assessment. During the biopsy procedure, two tissue cores should be collected and sent to RegenMed (Cayman) Ltd. for manufacture of NKA. If the patient experienced significant AE's/SAE's following biopsy (e.g., excessive bleeding, development of AV fistula) that, in the opinion of the PI would preclude safe injection, then the patient should be discontinued from the study. Biopsy samples that were obtained from previously enrolled patients in a Phase 1 trial and maintained in a frozen state will be used to generate the second dose of NKA that the patients are to receive

under this protocol. If there are not enough cells after thawing then these patients will be allowed to have the biopsy procedure completed for this study.

One week after receipt at Twin City Bio LLC's GMP facility in North Carolina, USA, RegenMed (Cayman) Ltd. will notify the site if the tissue received was of sufficient size and quality for manufacture of NKA. If results are positive, the site should confirm the scheduled date of injection. If the biopsy specimen is not able to be used for manufacture of NKA (for whatever reason), the patient should be discontinued from the study.

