11.1 Screening Assessments (Within 45 Days of the Biopsy)

All screening assessments should be scheduled in a timeframe that will allow for scheduling of the biopsy within 45 days of the first screening assessment conducted specifically for this protocol. For example, if a patient signs the consent and then goes to the laboratory for his/her blood draw two days later, then the date of the blood draw would be considered the date of the first screening assessment (not the date the ICF was signed). An MRI study should be conducted as part of the screening assessments. If the patient changes his/her mind after signing the ICF and refuses to have the MRI, then the patient must be discontinued from the study as the MRI will be used to define the dose of NKA.

To qualify for participation in the study, a patient's GFR must be between 20 - 50 mL/min/1.73m² inclusive. To define the GFR for entry criteria, the site should use the eGFR assessed during screening procedures and calculated using sCr and the CKD-EPI equation. If a patient does not meet a specific eligibility criterion, but the Investigator believes that the patient would be an excellent candidate for the trial, then that criterion may be reassessed one time. In general, a patient who does not qualify may be rescreened once as long as the Investigator has sufficient clinical justification for rescreening the patient. If the Investigator has any questions concerning appropriateness of rescreening a patient, then he/she should contact the Medical Monitor.

If, for whatever reason, the biopsy cannot be conducted within 45 days of the screening assessments, then the PI and Medical Monitor should discuss and agree upon the need for repeating screening assessments on a case by case basis. In some cases (e.g., if the biopsy will be a few days out of the protocol specified window), the laboratory assessments performed between 1 and 3 days before the biopsy may be used in place of the screening assessments to satisfy final eligibility criteria. In some cases, it may not be appropriate or necessary to repeat the clinical diagnostic procedures including the ECG or MRI studies.

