11.2 Biopsy (4 to 14 Weeks before Injection)

The biopsy should be scheduled within 45 days following the first screening assessment. The biopsy should be scheduled so that the injection procedure can be scheduled at 4 weeks or later. Due to shipping and manufacturing schedules, the preferred days for collecting the biopsy are Wednesday or Thursday. Biopsies should not be collected on a Friday.

Patients should report to the site one to three days before the biopsy for pre-biopsy assessments. As much as possible, pre-biopsy laboratory samples may be collected and assessed to verify patient eligibility prior to biopsy.

Following final review of appropriate eligibility criteria, the biopsy should be performed as described below in Section 12.5.1. The biopsy should be sent to RegenMed (Cayman) Ltd. in the shipping container provided by RegenMed (Cayman) Ltd. according to procedures detailed in the Study Reference Manual. After the biopsy, the patient should remain in the hospital overnight for observation. As long as any biopsy-related AEs have resolved, stabilized, or returned to baseline, the patient may be discharged the same day as biopsy per site standard practice.

Once the biopsy is received at RegenMed (Cayman) Ltd., the biopsy will be assessed and processed according to RegenMed (Cayman) Ltd.'s SOPs for product manufacturing. One to two weeks after receiving the biopsy in North Carolina, RegenMed (Cayman) Ltd. will notify the site concerning the adequacy of the sample for manufacture of NKA. Following the notification to proceed, the site can confirm the injection date. If the biopsy cannot be used for manufacture of NKA, the patient should be discontinued from the study.

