14.7.3 Laboratory Evaluations

Baseline values will be collected immediately prior to injection. Observed and change from baseline laboratory data will be summarized using a typical 8-number summary (sample size, mean, standard deviation, median, Q1, Q3, minimum, and maximum) for continuous variables and frequency and proportion for categorical variables. These summaries will be produced for both the FAS and the Injection analysis set. Generating inferential statistics is not planned.

Graded laboratory abnormalities will be defined using the NCI CTCAE grading scheme as defined in Section 12.3. Incidence of treatment-emergent laboratory abnormalities, defined as values that increase at least 1 toxicity grade from baseline at any time post baseline up to six months post-injection will be summarized. If baseline data are missing, then the latest value collected between biopsy and injection will be used as the baseline value. If baseline and pre-injection data are missing, then any graded abnormality, i.e., at least a Grade 1, will be considered treatment emergent.

Laboratory data summaries will be provided for both the FAS and the Injection analysis set. There are no plans to generate inferential statistics, except for variables concerning the rate of renal insufficiency progression. A paired t-test may be performed to assess the change in the rate of progression of renal insufficiency. Laboratory data will be provided in a data listing.

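### Two separate minor errors: schedule footnote 1 counts the 45-day screening window from injection instead of biopsy, and section 14.7.3 accepts no baseline for 24-hour urine or HbA1c in biopsied patients

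*Combined protocol and SAP*

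**What the plan says.** **Screening window.** Footnote 1 of the new-patient laparoscopic schedule reads "Screening assessments should be conducted within 45 days before the injection; if assessments fall outside of the 45 day window, rescreening should be conducted" and refers the reader to section 11.1. The new-patient percutaneous and second-dose laparoscopic schedules carry the same footnote, and the laboratory schedule (section 4) has an equivalent one: "Screening assessments should be conducted within the 45 days prior to the injection". The column that the footnote annotates is headed "≤45d pre- biopsy". Section 9 says that "a biopsy of the left/right kidney should be taken within 45 days of the first screening assessment", and section 11.2 gives the same window. Section 11.1 has the biopsy in its heading, and its rule on repeating assessments applies when "the biopsy cannot be conducted within 45 days of the screening assessments". The heading of section 11.2 puts the biopsy 4 to 14 weeks before injection.

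**Baseline.** Section 14.7.3 states: "Baseline values will be collected immediately prior to injection". Its paragraph on treatment-emergent laboratory abnormalities adds two rules. If baseline is missing, the most recent result from the biopsy-to-injection interval stands in. If that is missing too, every graded abnormality counts as treatment-emergent. The period for these abnormalities ends six months after injection. The laboratory schedule marks 24-hour urine at Screening and then at months 3, 9, 12, 15 and 18. It marks HbA1c at Screening and then at months 12, 18, 30 and 42. Neither test is marked at the Day -14 to -10 visit or on Day 0.

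**The concern.** On the first point, a site that screens and biopsies a patient as section 11 directs will usually be outside footnote 1. The footnote then calls for rescreening, but the section it cites deals only with a late biopsy. It does not say which tests a patient biopsied on time should repeat, or when, and the schedules have no column for doing so.

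On the second point, proteinuria is a named exploratory outcome, and section 14.7.3 promises change-from-baseline summaries of laboratory data. A screening result obtained before the biopsy meets neither the baseline definition nor the stand-in rule. Inclusion criterion 5 requires albuminuria at entry, so a rule that treats every graded abnormality as new when baseline is missing could report existing disease as emergent.

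**Working it through.** The plan states no figure to reproduce here. The check is date arithmetic plus a reading of the laboratory schedule.

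**1. Window**

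Inputs: *s* = days from first screening assessment to biopsy, 0 to 45 (sections 9, 11.1, 11.2). *b* = days from biopsy to injection, 4 × 7 = 28 to 14 × 7 = 98 (section 11.2). Footnote 1 requires *s* + *b* ≤ 45.

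- Range allowed by section 11: 0 + 28 = 28 to 45 + 98 = 143 days from screening to injection.
- Permitted values of *b*: 98 − 28 + 1 = 71. Values above 45: 98 − 45 = 53. Share: 53/71 = 74.6%. For these no pre-biopsy screening can meet footnote 1.
- For the other 18 values (28 to 45), screening must be at most 45 − *b* days before the biopsy: 17 days at *b* = 28, falling to 0 at *b* = 45.
- Date pairs that meet both rules: 18 + 17 + … + 1 = 171 of 46 × 71 = 3,266, or 5.2%. With *s* at least 1: 153 of 3,195 = 4.8%. With *s* at least 3: 120 of 3,053 = 3.9%.

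The last line counts calendar combinations without the weekday limits in sections 11.2 and 11.3. It does not estimate a share of patients.

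**2. Baseline**

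| Test | Collections before injection | Next collection | Meets 14.7.3 in a biopsied patient? |
|---|---|---|---|
| 24-hour urine | Screening | Month 3 | No |
| HbA1c | Screening | Month 12 | No |
| Spot urine | Screening, pre-biopsy, Day -14 to -10 | Day 7 | Yes |
| Renal chemistry, including creatinine | Screening, pre-biopsy, day after biopsy, Day -14 to -10, Day 0 | During the hospital stay, or Day 7 | Yes |

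The gap follows from the schedule and section 14.7.3 alone. Date pairs that satisfy both windows still leave the two tests without a qualifying value. Moving footnote 1 to the biopsy also leaves the gap open. A full rescreen after biopsy would fill it for the stand-in rule, but only as a side effect.

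**3. What falls inside the six-month period**

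Counted from the first injection, the month-3 24-hour urine is inside and the month-12 HbA1c is outside. The possible mislabelling therefore concerns 24-hour urine. With a baseline, a result must worsen by one grade or more to count. Without one, Grade 1 is enough.

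**4. Patients concerned**

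Up to 30 are injected, of whom at most 7 come from Phase 1 (section 6). New patients at full enrollment: 30 − 7 = 23 at least, all needing a study biopsy.

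**The case against.** Footnote 1 is probably a slip of one word. It defers to section 11.1, and every other statement of the window names the biopsy. The protocol confuses the two words elsewhere: the biopsy procedure in section 12.5.1 gives pain guidance for after the injection. This stands as a reason to call the error minor. It does not remove it, because the footnote recurs in four schedules and the injection anchor is the workable one for returning patients who need no biopsy.

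A reader might infer that rescreening is wholly undefined and that some sites will inject on old screening values. The documents do not support that. Section 10.1 has eligibility reviewed again before the biopsy and at Day -14 to -10. The laboratory schedule repeats chemistry, hematology, coagulation and spot urine at that visit, and virology just before the biopsy. Section 11.1 leaves repeat decisions to the investigator and Medical Monitor, and section 11.3 says what happens when eligibility is lost. Among the screening tests at issue, only HbA1c, 24-hour urine and MRI are not repeated.

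On baseline, the stand-in rule sits in the treatment-emergent paragraph, so applying it to change summaries is an inference. That is fair, but the main definition excludes a screening value by itself. It is also fair that the protocol gives no grading cut-points and that inclusion criterion 5 sets an albumin threshold, not a grade. The mislabelling is therefore conditional on the test being graded, although section 12.3 says that laboratory results will be.

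**Conclusion.** Both errors are real, separate and minor. Footnote 1 contradicts its own column header and three sections, and it cannot be met without a post-biopsy rescreen on 53 of 71 permitted biopsy days. Independently, 24-hour urine and HbA1c have no baseline that section 14.7.3 accepts in patients biopsied under this protocol.

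Three stronger readings should be set aside. The footnote does not cause the baseline gap. The 5% is a count of dates, and the documents do not give the actual spread of intervals. The primary efficacy measures are not affected, since creatinine, eGFR and the spot-urine ratios all have results between biopsy and injection. The schedule footnote that allows MRI at any time up to injection, and the synopsis headings that omit the pre-biopsy review, are clerical only.

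The conclusion rests on three assumptions: the column positions in the laboratory schedule, read from extracted text, are right; the six-month period runs from the first injection; and the mislabelling arises only if 24-hour urine is graded.

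**What to change.** Make both changes together, because the first alone leaves the baseline gap open.

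- **Footnote 1, in every schedule that carries it:** for patients having a study biopsy, screening falls within 45 days before the biopsy (section 11.1); for returning patients with no biopsy, within 45 days before the injection.
- **Section 14.7.3:** define baseline as the latest value before the first injection under this protocol, screening included, and report the age of that value for 24-hour urine and HbA1c.
- **Optional:** add HbA1c to the Day -14 to -10 blood draw.

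The cost is one footnote in several tables and one sentence in section 14.7.3. No new visit or procedure is needed. The optional step adds one analyte to blood that is already being drawn. The MRI footnote and synopsis headings can be tidied in the same revision.
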